***Flexible Guidelines for PRC Sessions (12-weeks)***

Week(s)	Frequency & Content
1	First session: Introduction to PRC sessions. PRC and patient discuss meeting time and locations, boundaries, and what the PRC's role is and is not. The PRC may also share their own story and experiences to engage the patient.
2 – 4	Weekly sessions: The PRC and patient meet approximately weekly. The PRC's goal is to help the patient navigate challenges they may be experiencing in engaging in HIV/SU care . The PRC may do this by providing psychoeducation around SU and HIV, using basic counselling skills (e.g., motivational interviewing, problem-solving therapy, behavioural activation), and supporting the patient in their recovery journey. The PRC may also share his/her own experiences throughout to engage the patient.
5 – 8	Session every other week: The PRC and patient will meet approximately every other week. The PRC will continue to support the patient in their recovery and motivate them to re-engage in HIV care and engage in SUD treatment.
9 – 12	Sessions as needed: In the final month, the PRC and patient together will determine how many sessions are needed. The PRC's goal this month will be to help the patient re-engage in HIV care and SUD treatment (if needed, if they have not already) and help them transition to using resources other than the PRC to support them in their recovery (e.g. peer support groups in the community).

Patient 3MFU Assessment. Approximately 3-months after their baseline assessment, patient participants will be asked to complete a 3MFU assessment. The 3MFU assessment consists of the same self-report questions around SU, HIV, and stigma that were asked at the baseline assessment. Additionally, patients in the Siyakhana condition (i.e., patients who had the opportunity to meet with a PRC) will also be asked to complete the Feasibility, Acceptability, and Appropriateness subscales of an Implementation & Dissemination measure.

12 to 24 weeks (3-6 months) post-baseline. Following the active treatment phase (which lasts approximately 12-weeks post-baseline), all participants will continue to receive their usual care. Participants in the intervention COPC will have the option to receive optional “booster sessions” with the PRC. These optional sessions will review material previously covered in normal sessions.

**Patient 6MFU Assessment.** Approximately 6-months after their baseline assessment, patient participants will be asked to complete a 6MFU assessment. The 6MFU assessment consists of the same self-report questions around SU, HIV, and stigma that were assessed at the baseline assessment. Additionally, patients in the Siyakhana condition (i.e., patients who had the opportunity to meet with a PRC) will also be asked to complete the Feasibility, Acceptability, and Appropriateness subscales of an Implementation & Dissemination measure.

**Qualitative Interviews.** After their 6MFU, all participants in the Siyakhana condition will be invited to participate in an individual, semi-structured interview.

**Stigma.** As part of a sub-study (R36DA057167), one part of the interview will assess patient perspectives on internalized SU stigma, potentially intersecting stigmas (e.g., HIV, gender, religion, ethnicity) from multiple levels (e.g., self, providers, community), experiences with the PRC, engagement in HIV and SU care, and relations between all these topics. The key domains of these interviews are perspectives on: (a) internalized SU stigma; (b) intersecting stigmas from multiple levels; (c) the PRC; (d) engagement in care; and (e) how these domains relate.

**Implementation.** As part of the current study, the second part of the interview will assess patients' perspectives on the implementation of the study. The main domains of interest will be feasibility and acceptability. However, other implementation domains, such as reach, adoption, and appropriateness, will also be assessed.

### **3.1.3 Stakeholders (Qualitative Interviews): Procedures**

Potentially eligible NGO stakeholders will be screened for eligibility. If eligible and interested in participating, they will undergo informed consent procedures. As part of this process, participants will be informed of all the potential risks and benefits to taking part in the one-time interview. Participants will be reminded that participation is voluntary and that they can decline to answer any questions that they are not comfortable answering and that they can withdraw from the study at any point. They will also consent to having the interview audio-recorded.

### **3.1.4 Additional Procedures**

We recognize the importance of ongoing support to PRCs in their recovery. Therefore, we have come up with strategies to monitor and support PRCs' ongoing recovery and self-care. We have successfully used these and similar strategies in previous studies.

**Recovery Stability:** All PRCs in this study will be well-established in their recovery (i.e., have been in self-reported recovery for at least one to two years, which is the threshold most commonly used in other settings for the PRC role). All PRCs hired will be selected based on their recovery length as well as supports for ongoing recovery.

**Ongoing Supervision:** The PRC(s) will receive regular (i.e., weekly or biweekly) supervision from the study team. The PRC(s) main supervisor will be a study team member who has previously worked with PRCs and is familiar on how to supervise this role. The supervisor will help the PRC monitor and reflect on their own recovery during supervision sessions, with ongoing attention to self-care following best practices for supervising PRCs.

## **Participant Compensation**

### **3.1.1 COPC HCWs: Compensation**

Initially, HCW participants did not receive monetary compensation for their trainings or assessments. The rationale for not providing monetary compensation for trainings was that participation in trainings is a regular part of their professional development, and trainings were conducted during usual working hours (time negotiated with organization that oversees COPC). Attendees were provided with meals during trainings and received reimbursement for travel (or were provided with travel) if they had to travel outside of their normal work commute for trainings. The rationale for not providing monetary compensation for assessments was similar – assessments were conducted during normal work hours and at their place of work. However, based on participant feedback, an amendment was approved so that HCW participants will be reimbursed R150 rand for completing a 6MFU, and for completing a qualitative interview.

### **3.1.2 COPC Patients: Compensation**

Patients will be compensated 150 Rand for each assessment (baseline, 3MFU, 6MFU) they complete. They will be compensated an additional 150 Rand for completing a semi-structured interview after the 6MFU.

### **3.1.3 Stakeholders (Qualitative Interviews): Compensation**

The stakeholders participating in the interviews will receive a 150 Rand gift voucher for consenting and completing the semi-structured qualitative interview.

#### **Phone**

All assessments and interviews may be completed in-person or over the phone. If over the phone, the research assistants will ask the participant if they feel free talking freely before beginning.

Allowing assessments and interviews to occur in-person or over the phone will allow for more flexibility around scheduling. As patients living with HIV who have disengaged from care and are using substances is a hard-to-reach population, this flexibility may allow us to recruit and retain more patients.

## 4. STATISTICAL ANALYSIS PLAN

### Type and Purpose of Data

The purpose of this pilot hybrid Type 1 implementation-effectiveness trial is to examine the pilot effectiveness (primary) and implementation (secondary) of our adapted PRC model. This study will collect quantitative (self-report assessments) and qualitative (semi-structured interviews) data. Additionally, HIV and attendance-related data will be extracted from patients' medical records, and attendance data will be extracted from patients' SUD treatment records.

### Effectiveness Outcomes

#### 4.1.1 Primary Outcome: HCW Stigma Towards SU

HCW stigma towards SUD will be measured using the Social Distance Scale (SDS), a well-validated measure of stigma used to capture health-related stigma across conditions and has been recommended for assessing mental health stigma among healthcare providers.

A total SDS score will be calculated to represent HCW stigma towards the target population at each time point, with higher scores indicating greater desire for social distance. First, we will conduct descriptive analyses (e.g., mean, standard deviation) to summarize the CHW stigma, using the continuous SDS score. The data distribution will be assessed to see whether the underlying assumptions are met (e.g., normality). Then we will examine the trajectory of HCW SUD stigma scores over time across the two conditions using a generalized linear mixed model, which includes all data points. The primary parameter of interest will be the interaction between time and condition to test whether changes in SUD stigma over time differ between the two groups.

Data will be analyzed over both three-months (3MFU) and six-months (6MFU). The primary timepoint is the 3MFU.

#### 4.1.2 Other Outcome: Patient Engagement in HIV Care

Throughout the study, patients' medical records will be monitored and clinic attendance data will be extracted.

We will compare the rate of re-engagement in HIV care in the Siyakhana condition to rate of re-engagement in HIV care in the ETAU condition. Our primary analysis will be a logistic regression examining re-engagement in care by group. We will examine engagement both between baseline and the 3MFU, and between baseline and the 6MFU. To supplement this dichotomous measure, we will also conduct a Poisson regression model to examine number of clinic visits by group over 3 and 6 months, and a Cox Proportional Hazard survival analysis to model time to re-engagement by group.

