#### **Rationale for Enrolment Numbers.**

As this is a pilot study with the primary goal of establishing feasibility and acceptability, we view our effectiveness effect size as preliminary. However, based on prior work in this population and with PRCs, we expect to find a small improvement in patient re-engagement in care in enhanced treatment as usual (ETAU; previous studies have found about 14% re-engagement in ETAU) and a larger improvement in the PRC condition (previous studies have found 66-89% improvement). Assuming ETAU re-engages at an even higher rate (i.e., 24%), and Siyakhana (PRC condition) re-engages at the low end of previous studies (i.e., 66%), enrolling 50 patients will give us approximately 85% power to detect a difference in patient re-engagement after accounting for up to 20% attrition and/or missing records.

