### 3.1.2 COPC Patients: Procedures

Study procedures for patient participants in the Pilot PRC Study are described below and illustrated in Figure 2.

**Patient Screening & Enrolment.** At least once a week, the study team will consult with enrolled COPC HCWs on patients who may be interested in participating in the study. The study team will contact these patients and briefly tell them about the study. If a patient is still interested in potentially participating, the study members will officially screen the patient. If the patient is still interested in participating after screening and met all eligibility criteria, a staff member will complete the informed consent process with the patient as soon as possible. The consent form will include all study procedures and state that we are seeking approval to extract information from medical records (i.e., information related to clinic visits (dates, attendance), HIV (viral load, CD4 count), care for other chronic diseases, referrals to other programs including SU treatment programs, etc.). It will also state that we are seeking approval to see if they attended local publicly funded SU treatment programs (date(s) of attendance, location(s) attended), provided through the South African Community Epidemiology Network on Drug Use (SACENDU). Finally, it will state that the study will only collect medical record and SU treatment program attendance data between the date of their baseline assessment and the date of 6MFU.

**Patient Baseline Assessment:** Upon completing informed consent, all patients will be asked to complete a self-report baseline assessment with a study team member. Ideally the baseline assessment will be completed immediately after informed consent is given. However, if the patient is unable to complete the baseline assessment immediately after consent, a time to complete the assessment will be scheduled for as soon as possible. The patient baseline assessment consists of self-report questions around demographics, SU, HIV, and stigma. After the baseline assessment, all patient participants will be given another referral to the nearest free SUD treatment program(s) (for example, the Help Me Network).

[figure not shown]
**Patient Active Treatment Phase: 0 to 12 weeks post-baseline.** Following the completion of the patient baseline assessment, the below procedures will occur.

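### The three patient engagement models contain group only, so measured baseline differences between two non-randomised patient groups pass into the estimate; one or two collected covariates should be prespecified

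*Combined protocol and SAP*

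**What the plan says.** Section 4.1.2 (Other Outcome: Patient Engagement in HIV Care) gives three analyses. For the yes/no outcome: "Our primary analysis will be a logistic regression examining re-engagement in care by group". Visit counts, the first supplementary measure, are handled by this method: "Poisson regression model to examine number of clinic visits by group over 3 and 6 months". The remaining supplementary analysis concerns timing: "Cox Proportional Hazard survival analysis to model time to re-engagement by group". Group is the only term named in each. No baseline covariate and no adjusted sensitivity analysis for patients is named elsewhere.

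Baseline data will exist. Section 3.1.2 (COPC Patients: Procedures) says: "The patient baseline assessment consists of self-report questions around demographics, SU, HIV, and stigma". Clinic records cannot supply attendance history, because of the limit that the same section puts on extraction: "only collect medical record and SU treatment program attendance data between the date of their baseline assessment and the date of 6MFU".

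Case mix is addressed only at team level: the Aims in section 3 describe the two teams as matched on staffing and patient population. Section 3.1.1 (COPC HCWs: Procedures) allocates one team to each arm by a coin flip, and training follows. Section 3.1.5 has patients screened and referred by HCWs after that training. Section 3.1.1 adds that Siyakhana HCWs know enrolled patients will be invited to meet the peer recovery coach (PRC).

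**The concern.** The protocol itself treats the unused variables as prognostic. Its Background and Rationale links untreated SU disorder to worse engagement in HIV care and describes internalised SU stigma as a barrier to it. The patient eligibility table requires HIV and a CAGE score of at least 2, but not being out of care, so enrolled patients can differ both in SU severity and in how engaged they already are.

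With about 25 patients per team, differences in such factors are expected by sampling alone. In this design they can also be systematic, since recruitment follows allocation and runs through staff who know it. A group-only model attributes all of this to the PRC. Engagement is an Other outcome, but it is the only outcome with a power calculation, and the estimate will inform later versions of the model.

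**Working it through.** **Inputs from the documents.** 50 patients, 25 per team; up to 20% attrition or missing records, so 25 × 0.8 = 20 evaluable per arm; assumed re-engagement 24% (ETAU) and 66% (Siyakhana), a difference of 42 points. Alpha is not stated; 0.05 two-sided is assumed. The documents give no covariate-outcome association, so it is assumed as an odds ratio (OR) per SD of 1, 1.5, 2 or 3.

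**The plan's own figure.** The enrolment rationale says "enrolling 50 patients will give us approximately 85% power". With 20 per arm, the unpooled standard error is √(0.24×0.76/20 + 0.66×0.34/20) = 0.1426, and power is Φ(0.42/0.1426 − 1.96) = 83.8%, close to the stated value. The exact power of the likelihood-ratio test from a group-only logistic model is 76.9%. That gap is a separate matter; 77% is the reference for the comparison below.

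**Size of chance imbalance.** For a standardised covariate, the difference in arm means has SD √(2/n).
- 25 per arm: SD 0.283; 95% range ±0.55 SD. For a binary factor with 50% prevalence, 1.96 × √(0.5/25) = ±28 points.
- 20 per arm: SD 0.316; 95% range ±0.62 SD, or ±31 points.
- An imbalance of at least 0.5 SD in either direction has probability 2 × [1 − Φ(0.5/0.283)] = 8% at 25 per arm and 2 × [1 − Φ(0.5/0.316)] = 11% at 20 per arm. This assumes simple random sampling from one population, which the recruitment route does not guarantee.

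**Effect on the estimate.** Take logit P(engaged) = a + ln(OR)·x, with x standard normal and a set so that the marginal rate is 24%. Shift x by d in one arm with no intervention effect. The false risk difference, in points, is:

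| OR per SD | d = 0.2 | d = 0.3 | d = 0.5 |
|---|---|---|---|
| 1.5 | 1.5 | 2.2 | 3.8 |
| 2 | 2.4 | 3.7 | 6.3 |
| 3 | 3.5 | 5.3 | 9.2 |

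At d = 0.5 these are 9%, 15% and 22% of the planned 42 points (3.8/42, 6.3/42, 9.2/42).

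**Gain from adjusting.** Simulation of 6,000 trials per scenario, with one standardised covariate, no systematic imbalance and marginal rates of 24% and 66%. Variance is that of the standardised risk difference relative to the unadjusted one:

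| OR per SD | Variance ratio, 20 per arm | Variance ratio, 25 per arm | Power at 20 per arm (group only about 77%) |
|---|---|---|---|
| 1 | 1.03 | 1.02 | 79% |
| 1.5 | 0.99 | 0.98 | 80% |
| 2 | 0.94 | 0.95 | 82% |
| 3 | 0.88 | 0.84 | 86% |

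Under the null, the adjusted likelihood-ratio test rejected in about 6 to 7% of trials, against about 5% for the group-only test, so part of the power gain is not real. The useless covariate (OR 1) shows this: at 20 per arm, power rises from 77% to 79% while the variance gets worse.

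**On the logistic model's own scale there is no gain in standard error.** With a binary covariate at 50% prevalence, engagement of 60% with it and 20% without (OR 6), no intervention effect and 25 per arm, the mean standard error of the group log odds ratio rose from 0.59 unadjusted to about 0.67 adjusted.

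**How many covariates the data can carry.** Expected re-engaged patients: 20 × (0.24 + 0.66) = 18 of 40 evaluable, with 22 not re-engaged. That supports one or two covariates.

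**The case against.** The strongest reply is that this is an exploratory outcome in a pilot that calls its effect size preliminary and places its main focus at HCW level; an unadjusted analysis of such an outcome is acceptable. That stands as an argument about weight. It does not remove the case for naming a covariate in advance, which costs little and prevents selective adjustment once baseline tables are seen.

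Three stronger readings are tempting, and the documents do not support them.

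- *Chance imbalance both biases the estimate and widens the interval.* This counts one thing twice. Averaged over trials, chance imbalance produces no bias, and the unadjusted interval already reflects it; the shifts tabulated above are that same variance seen at a given imbalance. Only systematic imbalance is bias in the usual sense. The recruitment route makes that possible but does not show that it will occur.
- *Adjustment is worth a fixed number of extra patients.* With the OR 6 factor above, simulation gives a variance ratio of about 0.85, equivalent to 1/0.85 = 1.18, or some 18% more patients. That strength is assumed. At OR 1.5 per SD the saving is 1 to 2%, and for an irrelevant covariate there is a small loss.
- *Adjustment repairs the comparison.* With one team per arm, any team or clinic effect is identical to the intervention effect in the data. If a between-team difference remained (assumed intraclass correlation 0.01 to 0.05), type I error at 20 per arm would be about 6 to 12%, whatever patient covariates are fitted.

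Two practical objections also stand. The protocol describes the baseline HIV items only in general terms, so whether HIV-care or ART status is asked is unconfirmed. All patients have CAGE of at least 2, which may narrow the range of SU severity.

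**Conclusion.** The point holds as a matter of method: the three patient models name group only, plausible predictors are collected, and nothing in the plan uses them. The stake is a shift of about 4 to 9 points in the risk difference for a 0.5 SD imbalance, assuming an OR of 1.5 to 3 per SD and a 24% base rate. That is not enough to create the planned 42-point difference, but it is material to a pilot estimate that will inform later work. Precision is a secondary and uncertain benefit, and it is visible on the standardised risk difference or in test power, not in the standard error of the log odds ratio. A reader should not infer that the group-only models are invalid, or that adjusting them would yield an effect free of team differences. This is a worthwhile improvement to an Other outcome and does not bear on the trial's primary HCW analysis.

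**What to change.** In section 4.1.2, before outcome data are seen:

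1. Name one or two baseline covariates that are actually collected: an SU severity measure and, if the baseline form contains it, self-reported HIV-care status. Check the form first. Records before baseline will not be available to supply it.
2. Include them in the logistic, Poisson and Cox models, using a small-sample (penalised) fit for the logistic model. State how a missing covariate value is handled, since participants may decline questions.
3. Report a covariate-standardised risk difference with a confidence interval, and show the unadjusted result beside it.
4. State that adjustment removes only measured patient-level differences and cannot separate team from intervention.

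The cost is SAP wording, with no new data collection provided the chosen items are on the form. The statistical price is one or two degrees of freedom with about 18 expected re-engaged patients among 40 evaluable, a variance increase of about 2 to 3% if a single chosen covariate proves unrelated to the outcome, and type I error of about 6 to 7% if an ordinary likelihood-ratio test is used for the adjusted model.

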### **3.1.2 COPC Patient: Eligibility**

We aim to enroll  $N=50$  patient participants in this study ( $n=25$  patients per COPC team).

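### The Poisson regression of clinic visits has no stated dispersion safeguard, so its p-value could err in either direction depending on a visit frequency the documents do not give

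*Combined protocol and SAP*

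**What the plan says.** Section 4.1.2 concerns patient engagement in HIV care, which is classed as an Other outcome. Its lead analysis is binary: "Our primary analysis will be a logistic regression examining re-engagement in care by group". As supplements, the section adds a Cox model for time to re-engagement and a count model: "we will also conduct a Poisson regression model to examine number of clinic visits by group over 3 and 6 months". Nothing is said about over-dispersion, robust or quasi-Poisson standard errors, or a negative binomial fallback. The SAP's one distribution check is in section 4.1.1 and concerns the Social Distance Scale score of the health care workers.

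The re-engagement rates come from the rationale for patient enrolment numbers under 3.1.2 (COPC Patient: Eligibility): "Assuming ETAU re-engages at an even higher rate (i.e., 24%), and Siyakhana (PRC condition) re-engages at the low end of previous studies (i.e., 66" per cent. That paragraph claims "approximately 85% power to detect a difference in patient re-engagement after accounting for up to 20% attrition and/or missing records" with 50 patients, 25 per team. No section gives the expected number of visits per patient or its variance.

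The consent paragraph under 3.1.2 (COPC Patients: Procedures) lists the records to be extracted, including "information related to clinic visits (dates, attendance), HIV (viral load, CD4 count), care for other chronic diseases".

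**The concern.** Clinic-visit counts in a hard-to-reach group often combine many patients who never attend with a smaller group who attend several times. If that happens here, the variance exceeds the mean, the model-based Poisson standard error of the log rate ratio is too small, and the test rejects too often. The count analysis is there to support the yes/no result, so a spuriously small p-value could seem to corroborate a re-engagement effect in a pilot whose findings are meant to inform later, powered work. If re-engaged patients attend about once each, the error runs the other way and the test is very conservative.

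**Working it through.** **Inputs from the documents.** Re-engagement p = 24% (ETAU) and 66% (Siyakhana); 25 patients per team; up to 20% loss, so 25 × 0.8 = 20 per arm analysed.

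**Assumptions.** Two-sided 5% (the documents state neither level nor sidedness). Mean visits per re-engaged patient, m, is not given, so a range is shown. Unless stated otherwise, visits among the re-engaged follow 1 + Poisson(m − 1), with variance v = m − 1.

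**1. The plan's own figure.** Power for 24% versus 66% at 20 per arm, unpooled normal approximation: SE = √(0.24×0.76/20 + 0.66×0.34/20) = 0.1426; 0.42/0.1426 − 1.96 = 0.985; power 83.8%, close to the stated 85%. The pooled version gives 78.3%. This concerns the binary outcome and matters here only as the source of the two rates.

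**2. Do the rates alone contradict Poisson?** No. A Poisson count with 76% zeros has mean −ln 0.76 = 0.274, and one with 34% zeros has mean −ln 0.34 = 1.079. Visits per re-engaged patient are then 0.274/0.24 = 1.14 and 1.079/0.66 = 1.63. Many zeros are compatible with variance equal to the mean.

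**3. When does over-dispersion start?** Variance/mean = v/m + m(1 − p). Setting this to 1:
- 1 + Poisson visits: m = 1/√(1 − p), which is 1.15 at 24% and 1.71 at 66%.
- Identical visits for every re-engaged patient (v = 0): m = 1/(1 − p), which is 1.32 and 2.94.

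**4. Size of the standard-error problem (24% versus 66%, 20 per arm).** At m = 2:
- Variance/mean = 0.5 + 1.52 = 2.02 (ETAU) and 0.5 + 0.68 = 1.18 (Siyakhana).
- Model SE of the log rate ratio = √(1/9.6 + 1/26.4) = 0.377.
- True SE = √(2.02/9.6 + 1.18/26.4) = 0.505.
- Ratio = 1.34.

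At m = 3 the ratio is 1.62 and at m = 1 it is 0.80. With identical visits per re-engaged patient it is 1.14 at m = 2 and 1.39 at m = 3.

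**5. Type I error of the nominal 5% test.** Simulated with 100,000 trials per scenario, 20 per arm, both arms at the same p:

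| Mean visits m | Poisson Wald, p = 24% | Poisson Wald, p = 66% | Sandwich SE, normal reference, 24% / 66% |
|---|---|---|---|
| 1 | 0.7% | 0.1% | 1.4% / 3.4% |
| 2 | 14.5% | 6.8% | 4.7% / 5.0% |
| 3 | 24.5% | 13.2% | 4.3% / 4.7% |
| 4 | 30.6% | 17.7% | 3.9% / 4.5% |

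Replacing the normal reference by a t reference brings the sandwich test to about 4.5% or below throughout. With 25 per arm the Poisson figures are similar: 15.6%, 25.0% and 31.3% at 24%, and 6.8%, 13.0% and 17.7% at 66%, for m = 2, 3 and 4.

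**6. Sensitivity to the assumed spread.** If every re-engaged patient has exactly three visits, Poisson type I error is 19% at 24% re-engaging and 5% at 66%. With exactly two visits at 66% it is 1.6%.

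**The case against.** The strongest reply is that the over-dispersion is assumed. The documents give yes/no re-engagement rates only, and step 2 shows that Poisson counts can match both. A reader might infer that 24% and 66% imply many zeros plus repeat visits, and so that the standard errors must be wrong. The documents do not support that: visit frequency appears nowhere, and at one visit each the test is too cautious. The zero share is itself uncertain, because the eligibility table does not require patients to be out of HIV care. This part of the reply stands, and it makes the point conditional.

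It does not remove the point. Under the assumed spread, Poisson is well calibrated only in a narrow range of visit frequency that nothing in the plan supports. The count also adds to the yes/no measure mainly when patients return more than once, which is where the Poisson standard error tends to be too small.

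A reader might also infer from the consent paragraph that visits for other chronic diseases, or peer sessions held at the clinic, will be counted. The documents do not say so. Section 4.1.2 stands under an HIV-care heading, the consent list names clinic visits and other chronic care as separate items, and nothing says peer sessions enter the medical record. The wording is ambiguous, no more.

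Finally, naming Poisson regression does not rule out robust errors, and no decision rule hangs on this model. Both are fair, and they limit the weight of the point.

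**Conclusion.** The point holds in conditional form. The plan commits to a Poisson model with no stated protection against variance differing from the mean. If re-engaged patients average about two to four visits, with 1 + Poisson spread and 20 per arm, the nominal 5% test rejects roughly 7% to 31% of the time under no difference. If they average one visit, it rejects less than 1% of the time. The size and direction rest on the assumed visit frequency and spread.

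The consequence is limited. The rate-ratio estimate is unchanged, the model supplements a logistic regression for an Other outcome, and the primary outcome is health care worker stigma. It would be too strong to conclude that the trial's patient findings are invalid because of this model.

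It would also be too strong to say that a robust variance makes the p-value valid. One team per arm is assigned by coin flip, so team differences cannot be separated from the intervention. With an assumed between-team SD of 0.5 on the logit scale and two visits each, the robust t test still rejects 8.7% of the time at 24% re-engaging and 11.7% at 45%. The p-value stays exploratory. This is a cheap improvement.

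**What to change.** In section 4.1.2, keep the rate ratio from the log-linear count model, and specify robust (sandwich) standard errors with a t reference distribution at both 3 and 6 months. In the same sentence, state that the count is of HIV-care visits.

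The cost is one line of SAP wording and no new data. The downside is wider confidence intervals when counts are over-dispersed. The results text should describe the p-value as exploratory, since the change does nothing about having one team per arm.
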